## Protocol Synopsis

Title	A Phase I/II Study of Pembrolizumab in Combination with Ibrutinib for Advanced, Refractory Colorectal Cancers
Clinical study phase	Phase I/II
Study Agents	Ibrutinib PO Pembrolizumab IV
Background	
Colorectal cancer is one of the most common worldwide malignancies, with close to 50% of patients ultimately developing metastatic disease. There remains an urgent need for additional novel options for patients who have disease progression through standard therapies.
 
Pembrolizumab is an anti-PD1 that functions by inhibiting checkpoint inhibition and reversing T cell suppression. It has activity in advanced, refractory colorectal cancer in patients with microsatellite instability but not tumors that are mismatch repair proficient. However, mismatch repair deficient tumors comprise a minority of metastatic colorectal cancers and work is underway to allow a wider application of immunotherapy in this common disease.
 
Ibrutinib is primarily a BTK inhibitor which has been approved for the treatment of several hematologic malignancies. Recent pre-clinical data has shown that there might be a role for ibrutinib in the treatment of solid tumors through counteracting the immune tumor escape mechanism.
 
Because of the immune modulatory function of ibrutinib, it has been suggested that the addition of checkpoint inhibitors could potentially produce a synergistic tumor response. This has been evaluated and confirmed in pre-clinical mouse models of microsatellite stable colorectal cancers.

Rationale	With this pre-clinical rationale, we hypothesize that ibrutinib added to pembrolizumab will be a safe and effective combination in microsatellite stable colorectal cancers.


Study objectives
	
Primary Objective (Phase I Portion)
 
To determine the safety and tolerability, describe the dose-limiting toxicities (DLTs), and determine the maximum tolerated dose (MTD) (or the highest protocol-defined dose level in the absence of establishing an MTD) of ibrutinib in combination with pembrolizumab in subjects with advanced, refractory colorectal cancers.
 
Secondary Objectives (Phase I Portion) 1. To determine the efficacy of ibrutinib in combination with pembrolizumab based on Response Evaluation Criteria in Solid Tumors (RECIST) v1.12. To determine the efficacy of ibrutinib in combination with pembrolizumab based on the RECIST based immune-related response criteria (irRC)
 
Primary Objective (Phase II Portion)
 
To determine the efficacy of ibrutinib in combination with pembrolizumab based on Response Evaluation Criteria in Solid Tumors (RECIST) v1.1
 
Exploratory Objectives
 
 
1. To use the CancerPlex® panel to assess the neoantigen burden of the tumor. The resulting “immune signature” will be correlated with outcome in a descriptive analysis.
 
2. To use the Luminex cytokine profiling system to analyze the effect of this combination on the immune system
 

--------------------------------	---

Indication	Patients with advanced, refractory colorectal cancer
Diagnosis and main criteria for inclusion	
 
• Age <math>\geq</math>18 years of age.
 
• Histologically confirmed diagnosis of colorectal adenocarcinoma
 
• Measurable or non-measurable disease by Response Evaluation Criteria in Solid Tumors (RECIST) 1.1. Stage IV or recurrent disease is required.
 
• Patients must have received and progressed through or become intolerant to fluoropyrimidine, irinotecan, oxaliplatin, and bevacizumab, and if RAS wild type, cetuximab or panitumumab containing therapies. Prior therapy with regorafenib and/or TAS 102 is allowed
 
• ECOG Performance Score 0 or 1
 
• Estimated life expectancy > 3 months
 
• Adequate bone marrow, liver and renal function as assessed by the following: 
 
o Hemoglobin > 8.0 g/dl
 
o Absolute neutrophil count (ANC) > 1,000/mm^3 independent of growth factor support
 
o Platelet count > 100,000/mm^3
 
o Total bilirubin < 1.5 times ULN unless bilirubin rise is due to Gilbert's syndrome or of non-hepatic origin
 
o AST, ALT and Alkaline Phosphatase <math>\leq</math>2.5 times the ULN (<math>\leq</math>5 x ULN for patients with liver involvement)
 
o Creatinine clearance <math>\geq</math> 30 ml/min
 
 
 

Study design	
This is a phase I/II trial using the combination of ibrutinib and pembrolizumab in advanced, refractory colorectal cancer. This will be a 3+3 design with 2 dose cohorts.
 
Following the dose escalation phase, the phase II portion of the study will enroll 32 patients.

Number of subjects	42

Plan for statistical analysis	
Sample Size The planned sample size is 6-12 patients in the dose-exploration portion (phase I) and 32 patients in the phase II portion.
 
Phase I For the dose exploration phase, the number of subjects will depend upon the DLTs observed and the number of dose levels tested as the study progresses in accordance with a 3+3 design. 6-12 patients are expected to be enrolled. Additional subjects could be enrolled if dose de-escalations or expansion of dose exploration is needed.
 
Phase II For the phase II portion of this study, the primary endpoint will be disease control rate (CR + PR + SD) at 4 months. Patients will be accrued to the protocol according to a two-stage Minimax design. At least 1 of 18 patients must have disease control at 4 months in the first stage to proceed to the second stage. If the protocol proceeds to the second stage, at least 4 of 32 patients overall must have disease control at 4 months for the therapy to be considered effective We anticipate an attrition rate of 10%, so around 49 patients will be recruited. Based on previous trials, we expect to enroll 42 patients in 12 months.

--------------------------------------	---

## **1. Introduction**

### **1.1 Background**

Colorectal cancer is one of the most common worldwide malignancies, and close to 50% of patients ultimately develop metastatic disease. Over the last few decades, there has been significant progress in the treatment of metastatic disease with the introduction of cytotoxic agents like oxaliplatin and irinotecan as well as biologic agents like bevacizumab and cetuximab. The median survival of those with metastatic disease at diagnosis is now over 2 years. Many patients maintain good performance status even after exhausting standard therapies and there remains an urgent need for additional novel options for these patients.

In the refractory setting, the oral agent regorafenib has been approved based on the results of two phase III studies showing an overall survival (OS) benefit over best supportive care. However, drug toxicity is a significant concern, limiting the use of regorafenib. Recently TAS 102, an thymidine-based nucleic acid analogue, trifluridine, and a thymidine phosphorylase inhibitor, tipiracil hydrochloride, was approved based on a phase III study demonstrating modest overall survival (1.8 months) improvement against placebo. Once again toxicity (primarily neutropenia and diarrhea) is concerning. New approaches to the management of refractory disease with manageable toxicity represent a clinical unmet need for the majority of patients with advanced colorectal cancer.

### **1.2 Immunotherapy in colorectal cancer**

Tumors contain unique genetic alterations that provide antigens by which they can be identified by the immune system. These antigens should be recognized and killed by T cell receptors. Immune checkpoints are generally activated to allow for self-tolerance and prevent excess autoimmunity. The immune checkpoint inhibitors increase activation of the immune system and recognition of tumor cells for destruction.

Colorectal cancer has long been known to have an immunologic component as tumors with immune infiltration have overall better prognosis. However, immune checkpoint inhibitors and vaccine studies have generally not resulted in significant activity in colorectal tumors. Novel approaches using immunotherapy combinations are needed to better target these tumors.

### **1.3 Ibrutinib**

Ibrutinib is primarily a BTK inhibitor which has been FDA approved for the treatment of several hematologic malignancies including CLL, previously treated mantle cell lymphoma, and Waldenstrom's macroglobulinemia, Small lymphocytic lymphoma, Marginal Zone lymphoma and Graft versus host disease. Recent pre-clinical data has shown that there might be a role for ibrutinib in the treatment of solid tumors, including lung and breast cancers. Ibrutinib has been hypothesized to counteract the immune escape mechanism used by tumors wherein the Th2 response is promoted and Th1 response (associated with cytotoxicity) is suppressed.

## **Pre-clinical Experience**

Ibrutinib was initially evaluated in hematologic malignancies but has recently been looked at in solid tumors. BTK inhibition by ibrutinib is hypothesized to modulate the tumor microenvironment (Ibrutinib investigator's brochure). In breast cancer lines in vitro, ibrutinib was shown to have an inhibitory effect on tumor growth. In a pancreatic adenocarcinoma model, ibrutinib was found to inhibit tumor growth in vivo. There has also been activity shown in lung cancer cell lines and colon cancer mouse models.

## **Clinical Experience**

### *Clinical Pharmacokinetics*

Ibrutinib has been evaluated in human subjects in multiple studies at doses ranging from 140 mg to 840 mg per day. Co-administration of ibrutinib with strong CYP3A inhibitors like ketoconazole has been found to increase exposure of ibrutinib. Based on data for the effects of food, ibrutinib could be taken with or without food at approximately the same time each day.

### *Clinical Efficacy*

Ibrutinib has been FDA approved for the treatment of Chronic Lymphocytic Leukemia, including those tumors with a 17p deletion, previously treated Mantle Cell Lymphoma, and Waldenstrom's Macroglobulinemia based on the results of clinical studies.

### *Clinical Safety*

According to the IMBRUVICA USPI (6/2016), the most common adverse reactions ( $\geq 20\%$ ) in patients with B-cell malignancies (MCL, CLL/SLL, WM) were thrombocytopenia, diarrhea, anemia, neutropenia, musculoskeletal pain, fatigue, bruising, nausea, rash, hemorrhage and pyrexia. The warnings and precautions for ibrutinib include: hemorrhage, infections, cytopenias, atrial fibrillation, hypertension, second primary malignancies, tumor lysis syndrome, embryo-fetal toxicity.

## **1.4 Pembrolizumab**

Human tumors have multiple genetic alterations leading to neoantigens which should be recognized by the immune system of the host. However, cancer can dysregulate immune checkpoint proteins as a way of evading the host immune system and ensuring tumor survival. Immunotherapy in oncology has been evaluated as a means of upregulating the host immune system so that tumors can be recognized as foreign and endogenous anti-tumor immunity can attack tumor cells. Immune checkpoint pathway inhibitors such as anti-CTLA4 and anti-PD-1 antibodies have been evaluated in the treatment of a variety of tumors.

Programmed death 1 is a protein which limits T-cell activity in an effort to minimize autoimmunity. When activated by ligands, PD-1 along with its costimulatory protein B7, decrease T cell activity which can allow tumors to escape immune recognition. Antibodies against PD-1 have been developed in an effort to increase T cell activity.

Pembrolizumab is a potent humanized immunoglobulin G4 (IgG4) monoclonal antibody (mAb) with high specificity of binding to the PD-1 receptor, thus inhibiting its interaction with programmed cell death ligand 1 (PD-L1) and programmed cell death ligand 2 (PD-L2). Based on preclinical in vitro data, pembrolizumab has high affinity and potent receptor blocking activity for PD-1.

Pembrolizumab functions by inhibiting checkpoint inhibition and reversing T cell suppression. A recent study showed activity in advanced, refractory colorectal cancer in patients with microsatellite instability but not tumors that were mismatch repair proficient. The mechanism of action in these tumors is hypothesized to be that the increased immunogenicity of these highly mutated tumors provides multiple targets upon which the anti-PD1 agent can act. However, these tumors comprise only 2-4% of all metastatic colorectal cancers.

### **Pre-Clinical Experience**

Pembrolizumab has been found to enhance T-cell activity in blood cells in vitro (Pembrolizumab Investigator's Brochure). In addition, IL-2 and other cytokine production was enhanced. In addition, it was found to increase the antigen-specific recall response to tetanus toxoid in peripheral blood mononuclear cells from vaccinated individuals in vitro. In vivo, a pembrolizumab like antibody was tested as monotherapy in murine tumor models and found to inhibit tumor growth of a colon adenocarcinoma (Pembrolizumab Investigator's Brochure). In toxicology studies of Cynomolgus monkeys, pembrolizumab at doses up to 200mg/kg weekly or every other week resulted in no treatment related adverse effects.

### **Clinical Experience**

#### *Clinical Pharmacokinetics*

Pembrolizumab has been tested in several thousand human subjects with doses ranging from 1mg/kg to 10 mg/kg. Pembrolizumab has been found to have a low potential of eliciting anti-drug antibodies.

#### *Clinical Efficacy*

Pembrolizumab has been FDA approved for the treatment of metastatic melanoma and metastatic non-small cell lung cancer based on clinical trial results. The majority of responses have been durable and have exceeded 6 months. In melanoma, pembrolizumab has been approved in metastatic disease in the first line setting as well as after progression on ipilimumab or a BRAF inhibitor on patients with a BRAF mutation. In non-small cell lung cancer, it has been approved in advanced disease after progression on one prior treatment in patients whose tumor express PD-L1.

#### *Clinical Safety*

The safety profile is similar across tumor types and there has been no pattern of adverse effects with regards to incidence or severity based on dose level. The incidence of drug related adverse effects was generally low and included nausea, fatigue, and diarrhea. Grade 3-5 drug related

adverse events have included anemia increased LFTs, and pulmonary toxicity.

## 1.5 Rationale

Because of the immune modulatory function of ibrutinib, it has been suggested that the addition of checkpoint inhibitors like pembrolizumab could potentially produce a synergistic tumor response. This was initially evaluated in a mouse model of lymphoma, which showed that anti-PDL-1 therapy alone delayed tumor growth but was not curative. However, the combination of ibrutinib with anti-PDL1 resulted in about 50% of the mice being cured. This combination was then tested in colon and breast cancer mouse models and showed a similar synergistic effect. Interestingly, the colon mouse model (CT26) is not known to be associated with a microsatellite high phenotype. A similar study with the anti-CTLA4 agent ipilimumab showed synergy with ibrutinib, also in a colon mouse model.

As there is known synergy between immunotherapy agents and ibrutinib in microsatellite stable colon mouse models, we hypothesize that ibrutinib added to pembrolizumab will lead to a disease response and improve survival in microsatellite stable colorectal cancers.

The combination of pembrolizumab and ibrutinib is investigational as is for the treatment of colorectal cancer. On the basis of the data described above, we hypothesize that the combination of ibrutinib and pembrolizumab in refractory colorectal cancers will be safe and efficacious.

## 2. Study Objectives

### Primary Objective (Phase I)

To determine safety and tolerability, describe the dose-limiting toxicities (DLTs), and determine the maximum tolerated dose (MTD) (or the highest protocol-defined dose level in the absence of establishing an MTD) of ibrutinib in combination with pembrolizumab in subjects with advanced, refractory colorectal cancers.

### Secondary Objectives (Phase I)

1. To determine the efficacy of ibrutinib in combination with pembrolizumab based on Response Evaluation Criteria in Solid Tumors (RECIST) v1.1
2. To determine the efficacy of ibrutinib in combination with pembrolizumab based on the RECIST based immune-related response criteria (irRC)..
3. To determine overall survival

### Primary Objective (Phase II)

To determine the efficacy of ibrutinib in combination with pembrolizumab based on Response Evaluation Criteria in Solid Tumors (RECIST) v1.1

## **Exploratory Objective**

1. To use the immunohistochemical stains and HTG EdgeSeq ImmunoOncology Assay to assess the host immune response in tumor microenvironment. The resulting “immune gene expression profiles and immune cells profiles” will be correlated with clinical outcome in a descriptive analysis.
2. To use the Luminex Multiplex immunoassay and the flowcytometry, to analyze the effect of this combination on the immune system and immune cells in peripheral blood.

## **3. Study Design**

This is a phase I/II open-label trial to assess the safety, tolerability, and preliminary anti-tumor activity of pembrolizumab and ibrutinib in subjects with advanced, refractory colorectal cancer.

The study consists of two phases:

### **Escalation phase (Phase I)**

The objective of this phase is to investigate the safety, tolerability and recommend the dose of the combination. Ibrutinib and pembrolizumab will be concurrently administered in sequential cohorts of 3- 6 subjects with each receiving pembrolizumab 200 mg every 3 weeks (Q3W) and ibrutinib at doses of 420 mg daily ( cohort 0) and 560 mg daily (cohort 1) .

The first cohort will enroll a minimum of 3 subjects, according to a standard 3+3 design. If 0 out of the first 3 subjects in the first cohort experience a dose-limiting toxicity (DLT), then dose escalation will continue as planned. If 1 out of the first 3 subjects experience a DLT, then the cohort will be expanded to a total of 6 subjects, and if no more than 1 out of 6 subjects experiences a DLT in a given dose cohort, dose escalation will continue as planned. If  $\geq 2$  DLTs are observed in the first dose cohort, the principle investigator will discuss with Janssen on how to proceed. The DLT evaluation period will be defined as the time from the first dose of pembrolizumab and ibrutinib to 42 days after the first dose or if a subject experiences a DLT within this time period. A maximum of 2 cohorts is expected, making a total of approximately 12 evaluable subjects during the dose escalation phase.

### **Phase II (Phase II)**

The phase II portion of the study is to be conducted in patients with advanced, refractory colorectal cancer. The objective of this phase of study is to assess disease control rate (CR + PR+ SD) and further investigate the safety, tolerability and preliminary clinical activity of the combination at the recommended dose. 32 evaluable subjects with advanced, refractory colorectal cancer will be enrolled. Patients will be on treatment until unacceptable toxicity or disease progression for a maximum of 24 months. 32 subjects with microsatellite stable colorectal cancer will receive concurrent ibrutinib PO qdaily and pembrolizumab 200 mg IV Q3W beginning on Day 1 using the recommended dose of ibrutinib from the escalation phase to evaluate disease control rate and further evaluate safety, tolerability and preliminary evaluation

of clinical efficacy. Initiation of expansion arms with the recommended dose of ibrutinib in combination with pembrolizumab at 200 mg IV will be based on an adequate safety and tolerability profile of the combination from the escalation phase.

#### 4. Eligibility

##### 4.1 Inclusion Criteria

- Histologically confirmed diagnosis of colorectal adenocarcinoma
- Measurable or non-measurable disease by Response Evaluation Criteria in Solid Tumors (RECIST) 1.1. Stage IV or recurrent disease is required.
- Patients must have received and progressed through or become intolerant to fluoropyrimidine, irinotecan, oxaliplatin, and bevacizumab. If RAS wild type, patients should have received and progressed or become intolerant to the above as well as cetuximab or panitumumab containing therapies. Prior therapy with Regorafenib and/or TAS 102 is allowed
- ECOG Performance Score 0 or 1
- Estimated life expectancy > 3 months
- Adequate bone marrow, liver and renal function as assessed by the following:
  - o Hemoglobin > 8.0 g/dl
  - o Absolute neutrophil count (ANC) > 1,000/mm^3 independent of growth factor support
  - o Platelet count > 100,000/mm^3
  - o Total bilirubin < 1.5 times ULN unless bilirubin rise is due to Gilbert's syndrome or of non-hepatic origin
  - o AST, ALT and Alkaline Phosphatase ≤2.5 times the ULN (≤5 x ULN for patients with liver involvement)
  - o Creatinine clearance ≥ 30 ml/min
- Patients must not have had chemotherapy, major surgery, monoclonal antibody therapy or experimental therapy within the 21 days prior to the start of ibrutinib administration
- Women of childbearing potential must have a negative serum or urine pregnancy test performed within 7 days prior to the start of study drug. Post-menopausal women (defined as no menses for at least 1 year) and surgically sterilized women are not required to undergo a pregnancy test.
- Subjects (men and women) of childbearing potential must agree to use adequate contraception beginning at the signing of the ICF until at least 4 months for both females and males after the last dose of study drug. The definition of adequate contraception will be based on the judgment of the principal investigator or a designated associate.
- Subjects (men and women) must agree to not donate sperm (males) or eggs (females) during and up to 120 days after the last dose of study treatment.
- Subjects must be able to understand and be willing to sign the written informed consent form. A signed informed consent form must be appropriately obtained prior to the conduct of any trial-specific procedure. Subjects must be willing and able to comply with scheduled visits, treatment schedule, laboratory testing, and other study requirements.

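### The microsatellite stable restriction that Section 3 places on phase II is not carried into the eligibility criteria, and the 5% and 20% rates in Section 9.2 name no population

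*Combined protocol and SAP*

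**What the plan says.** Section 3, in its phase II paragraph, describes the 32 subjects twice. First: "32 evaluable subjects with advanced, refractory colorectal cancer will be enrolled". Then: "32 subjects with microsatellite stable colorectal cancer will receive concurrent ibrutinib PO qdaily".

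The hypothesis is about MSS disease. The synopsis rationale states "we hypothesize that ibrutinib added to pembrolizumab will be a safe and effective combination in microsatellite stable colorectal cancers", and Section 1.5 expects that "ibrutinib added to pembrolizumab will lead to a disease response and improve survival in microsatellite stable colorectal cancers". Section 1.5 then closes with a broader sentence, that "the combination of ibrutinib and pembrolizumab in refractory colorectal cancers will be safe and efficacious".

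The tumour criterion, in the synopsis and in Section 4.1, is "Histologically confirmed diagnosis of colorectal adenocarcinoma". Neither list, nor the exclusions in Section 4.2, sets a condition on microsatellite or mismatch-repair status. Section 4.2 does exclude prior checkpoint therapy. The phase I objective is also unrestricted: "ibrutinib in combination with pembrolizumab in subjects with advanced, refractory colorectal cancers".

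Section 1.4 explains why the status matters: "A recent study showed activity in advanced, refractory colorectal cancer in patients with microsatellite instability but not tumors that were mismatch repair proficient". It puts the microsatellite-unstable share at 2–4% of metastatic colorectal cancer.

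Section 9.2 gives a two-stage Minimax design: null rate 5%, target rate 20%, alpha 0.10 and beta 0.10. At least 1 of 18 patients must have disease control at 4 months to continue, and at least 4 of 32 for the therapy to be called effective. Six patients treated at the MTD are to be counted in phase II provided the treatment plan and eligibility are unchanged.

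**The concern.** Screening staff work from the eligibility list. A checkpoint-naive MSI-high patient who meets every line of Section 4 can be enrolled under that section, although Section 3 describes a population that leaves the patient out. Once enrolled and restaged, the patient counts toward both boundaries.

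The trial has no control arm, so the efficacy conclusion rests entirely on the comparison with 5%, and the boundaries are low. Disease control in an MSI-high patient is what Section 1.4 would lead one to expect from pembrolizumab alone. It says little about whether the combination works in MSS disease. Because Section 9.2 does not say whether 5% is an MSS or an all-comer rate, the reader cannot tell whether the stated alpha would still hold if such patients entered.

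The carry-over rule adds a smaller question: if phase I is unrestricted and phase II is MSS only, has eligibility changed, and do the six MTD patients count?

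**Working it through.** **Inputs from the protocol.** Section 9.2: n1 = 18, continue if at least 1; n = 32, success if at least 4; p0 = 0.05; p1 = 0.20; alpha 0.10; power 0.90. Section 1.4: MSI share f = 2–4%, stated for all metastatic disease.

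**Assumed input.** MSI-high disease control at 4 months, q = 30–80%. The documents give no figure.

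**1. The plan's own design.** P(success | p) = Σ over x1 ≥ 1 of Bin(x1; 18, p) × P(X2 ≥ 4 − x1; 14, p).
- p = 0.05: 0.0721 (limit 0.10).
- p = 0.20: 0.9015 (requirement 0.90).
- Stage 1 stop at 5%: 0.95^18 = 0.397.

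The design reproduces; the sample size is not in question.

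**2. Chance that at least one MSI-high patient enters if Section 4 alone governs,** 1 − (1 − f)^n:

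| n | f = 2% | f = 4% |
|---|---|---|
| 32 | 0.476 | 0.729 |
| 18 | 0.305 | 0.520 |
| 6 (MTD patients) | 0.114 | 0.217 |

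**3. False-success probability if 5% is an MSS rate.** The mixed rate is p = f·q + (1 − f)·0.05, put into the formula in step 1:

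| q | p, f = 2% | P(success) | p, f = 4% | P(success) |
|---|---|---|---|---|
| 30% | 0.055 | 0.095 | 0.060 | 0.120 |
| 40% | 0.057 | 0.105 | 0.064 | 0.143 |
| 60% | 0.061 | 0.126 | 0.072 | 0.192 |
| 80% | 0.065 | 0.148 | 0.080 | 0.246 |

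Seven of the eight cells exceed 0.10; the mildest does not.

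**4. How often an MSI-high patient alone carries stage 1, at q = 60%.** This is the chance that no MSS patient among the 18 has control, less the chance that nobody does: [1 − (1 − f)·0.05]^18 − [1 − (1 − f)·0.05 − f·q]^18.
- f = 2%: 0.951^18 − 0.939^18 = 0.405 − 0.322 = 0.083.
- f = 4%: 0.952^18 − 0.928^18 = 0.413 − 0.261 = 0.152.

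**5. Effect of a single case.** With one controlled MSI-high patient and the other 31 at 5%, false success is 0.201 if the patient is in stage 1 and 0.191 if in stage 2. At q = 60%, the chance of no controlled MSI-high patient among 32 is (1 − 0.6f)^32: 0.680 at f = 2% and 0.460 at f = 4%. Step 5 therefore describes an unfavourable trial, and step 3 the average.

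**6. Where nothing changes.** If only MSS patients enrol, or if 5% is the true all-comer rate, p = 0.05 and the result is 0.0721 again.

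**The case against.** The strongest reply is that this is an omission, not a contradiction. MSS cancer is a subset of advanced, refractory colorectal cancer, so the second sentence in Section 3 can be read as specifying the first. The closing sentence of Section 1.5 follows directly on the MSS hypothesis and need not signal an all-comer intent. No passage says that MSI-high patients are admitted. All of this stands.

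A reader might go further and infer that a site cannot comply with both Sections 3 and 4. The documents do not support that: Section 4 sets conditions a patient must meet and does not oblige the site to enrol everyone who meets them. A reader might also fault Sections 4.3.1 and 9.3 for lacking an MSS limit. Those sections operate on patients already enrolled and need not repeat eligibility.

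On redaction, blacked-out screening items could conceal an MSI or mismatch-repair test, which together with Section 3 might act as the restriction. The legible footnotes on archival tissue and blood cells suggest biomarker samples instead, but this cannot be settled. The criteria lists themselves are not redacted and contain no such condition.

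On carry-over, the condition in Section 9.2 can be read literally to mean that a new MSS restriction is a change in eligibility, so the six would not count. That reading is available, but the section does not state it.

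The gap between Section 3 and Section 4, and the unnamed population behind 5% and 20%, remain.

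**Conclusion.** The point holds as a gap that should be fixed: the MSS restriction in Section 3 and the hypothesis does not reach the eligibility criteria, and Section 9.2 does not say whose rate 5% is.

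The error-rate consequence is conditional. It requires that Section 4 alone governs enrolment, that 5% is an MSS rate, that the 2–4% share for all metastatic disease holds in this refractory population, and that MSI-high control lies in the assumed 30–80% range. Under all four, false success is 0.095–0.148 at a 2% share and 0.120–0.246 at 4%. At 60% control, an MSI-high patient is the only reason stage 1 passes in about 8% to 15% of trials.

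It would be too strong to say that the trial's alpha is inflated. With MSS-only enrolment, or an all-comer 5%, it stays at 0.072. In the all-comer case the remaining problem is interpretive: a positive pooled result would not cleanly support the MSS hypothesis.

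**What to change.** Reconcile Sections 3 and 4, Section 9.2 and the synopsis to one intended population.

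**If MSS is intended:**
- Add to the phase II criteria in Section 4.1 and the synopsis: tumour documented as microsatellite stable or mismatch-repair proficient.
- List that documentation among the screening items in Section 6.1 and the calendar.
- State in Section 9.2 that the 5% and 20% rates refer to MSS patients.
- State whether phase I patients treated at the MTD count toward the 32; only those documented MSS should.

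**If all-comers are intended:**
- Remove the MSS wording from Section 3.
- State that 5% is an all-comer rate.
- Report disease control by MSI status, and do not claim support for the MSS hypothesis from the pooled result.

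Either way, the 18/32 design and its boundaries stay as they are.

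**Cost.** The MSS option loses about 2–4% of eligible patients plus any whose status cannot be established; the calendar footnote provides for archival tissue only where it exists. With the synopsis attrition of 10%, 32 evaluable patients need 32/0.9 = 35.6 enrolled. Allowing for status, and assuming 0–20% unestablished, the range is 32/(0.98 × 0.9) = 36.3 to 32/(0.96 × 0.80 × 0.9) = 46.3 otherwise eligible patients. Up to six further phase II enrolments are needed if MTD patients cannot be carried over. The all-comer option costs wording changes and one table, with no extra patients. Neither option isolates ibrutinib's contribution, which a single-arm trial of the combination cannot do.
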